VA Office of Research and Development Results Record C0239-R

Title: Randomized Trial Comparison of Ototoxicity Monitoring Programs

ClinicalTrials.gov identifier: NCT02099786

Protocol; Document Date: 9-29-17

Experimental Methods

A. Subjects.

A1. Subject Recruitment: An estimated 320 patients from VA Portland Health Care System (VAPORHCS) receiving chemotherapy will be identified by a search of the upcoming chemotherapy unit appointment list, pharmacy list or by oncology referral including verbal referral and encrypted email. Additionally, approximately 120 healthy control subjects (Veterans and non-Veterans) not administered chemotherapy will also be recruited at the VAPORHCS from posted recruitment advertisements and from the NCRAR database of Veterans willing to participate in future hearing research projects. Potential chemotherapy patients will be accessed using electronic medical records (CPRS) to determine the diagnosis and treatment plan and to search for exclusionary criteria. If the potential subject is not excluded based on initial CPRS search, oncology personnel will approach the potential subject to determine his/her willingness to learn more about the study after hearing a brief description. The Program Evaluation (PE) audiologist will then talk with the patient, offer a more thorough explanation of the study, including the necessity for duplicate testing. If the potential subject remains interested in the project, informed consent will be obtained including an explanation of the goals of the study, requirements of the study protocol and the potential risks and benefits to the subject.

Initial testing to establish inclusion in the study and to provide the first PE will be done in a quiet area. After the evaluation, if the subject has met all further inclusion criteria, the subject will be randomized to a treatment arm: Standard of care (SOC) or Comprehensive Ototoxicity Monitoring Program for VA healthcare (COMP-VA). Study personnel will then be informed that a subject has been consented, tested, and assigned to a study arm and is ready to receive a baseline evaluation.

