C2a. Distortion Product Otoacoustic Emission Instrumentation for COMP-VA: Either the OtoID-based DPOAE testing (or cart system) can be used to collect DPOAEs.

C3. Other data to be gathered on study participants with cancer: Additional information obtained on each subject from the electronic medical records (CPRS) will be entered into the database, maintained by by study team members including a biostatistician and research assistant(s). Information to be obtained will include patient factors such as name, gender, age, type of cancer and staging, drug treatment variables such as cisplatin dose and dosing (intensity) and concomitant radiation dose and doublet medication and other information related to treatment and patient factors as required to accomplish the study goals. CPRS clinical progress notes will be monitored by a study team member on each subject (estimated n=80/yr) entered into either study arm in order to obtain Audiology Service utilization **for up to one year** post-randomization. In addition, in order to get a less biased estimate of audiological services utilization rates, an historical cohort comprised of all patients identified as receiving cisplatin approximately 3 years prior to the initiation of the study will be searched in CPRS and the cancer registry for audiological services used (estimated n=220 pts). We estimate approximately 300 patient records may be accessed to complete this search. These data may be combined with data from other studies done by these investigators in an IRB-approved manner.

A study team member may request providers' feedback in the form of a simple checklist (Oncology Practitioner Survey) provided to them at each treatment interval by a study team member.

We may also survey practitioners (oncologists, nurses, and audiologists) to assess their beliefs about ototoxicity monitoring practices using an anonymous beliefs questionnaire (i.e., no PHI or PII). This survey will be made available at 2 intervals.

In order to establish a benchmark for relapse-free survivorship from which to compare COMP-VA subjects' survivorship, we will be evaluated survivorship of Veterans with a diagnosis of cancers treated with cisplatin using the VA Cancer Registry (or other) which follows Veterans treated in VA for 5+ years following treatment. We will follow current study participants for cancer survivorship for approximately 2-3 years depending on enrollment date and resources available to do so.

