VA Office of Research and Development Results Record C0239-R

Title: Randomized Trial Comparison of Ototoxicity Monitoring Programs

ClinicalTrials.gov identifier: NCT02099786

Outcomes and Statistical Plan; Document Date: 9-29-17

Outcomes and Statistical Plan

Outcome Measures

The following outcomes were evaluated as a function of treatment arm.

1. **Hearing tests.** Rates of ototoxicity were evaluated using two criteria: (i) Ototoxic hearing shifts meeting the ASHA 1994 definition 20dB shift at one frequency; 10 dB shift at two consecutive frequencies or loss of response at three frequencies. (ii) Ototoxicity meeting the Cancer Institute Common Terminology Criteria for Adverse Events (CTCAE) Grade 1 or greater toxicity [hearing shift of 15-25 dB averaged at 2 contiguous test frequencies in at least one ear].
2. **Audiology rehabilitation service use.** This included: (i) service utilization to issue new hearing aids to subjects who were not hearing aid users at baseline; and (ii) technology update or hearing aid adjustment for previous hearing aid users. CPRS progress notes were monitored by the NCRAR Research Audiologist on each subject enrolled in the study in order to determine audiology rehabilitation service use for one year post-randomization. All audiology clinic visits were recorded by date and type of visit. Additionally, subjects were queried about aural rehabilitation service at each PE and interim phone calls.
3. **Quality of life measures.** Differences in the HHIA questionnaire score (or HHIE score as appropriate depending on the age of the subject) at PE 3 were evaluated.
4. **Survivorship** among subjects was also evaluated, defined as differences in rates of death during the study period.

Hypotheses to be Tested and Statistical Plan

1. *Use of COMP-VA will improve patients' hearing and quality of life outcomes without diminishing chances for survival.* Simple analysis will entail computing odds ratios and contrasting these between the COMP-VA and SOC groups. We will also fit a logistic regression model to the probability of ototoxicity (separately modeled for ASHA and CTCAE grade 1 or

greater) with randomization group assignment as predictor. *We anticipate that hearing loss progression will be less among COMP-VA subjects, meaning that, the COMP-VA group will have smaller 35 day and 1 year post-randomization hearing shifts compared to SOC patients.*

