2. *We hypothesize that COMP-VA will minimize some of the adverse effects of cisplatin treatment on Veterans' hearing-related quality of life, either through treatment modifications to diminish cisplatin-induced hearing loss or effective post-chemo audiological service delivery to limit the ill-effects of any pre-existing, new or worsened communication deficit.* We will conduct a contrast of perceived hearing handicap (HHIE or HHIA questionnaire administered at 1 year post-randomization), between patients randomized to COMP-VA and SOC. We will conduct a t-test with randomization arm as the contrast to test the importance of COMP-VA on perceived quality of life outcomes.

3. *Compared with patients randomized to SOC, patients randomized to COMP-VA will use Audiology rehabilitation services at a higher rate because of their greater awareness of new, increased or pre-existing communication deficits.* To test this hypothesis, we will contrast the probability of one or more audiology clinic rehabilitation visits using logistic regression with group membership as a factor.

4. *We anticipate that cisplatin patients given the COMP-VA intervention will fair no worse than SOC patients in terms of their survival.* This component of the study is framed as a non-inferiority trial. i.e. we require sufficient evidence to reject the null hypothesis that COMP-VA patients have lower one-year survival rates than patients treated under SOC. Analysis for non-inferiority trials using survival outcomes have been described and are easily computed using logistic regression output. We will require a non-inferiority margin of no more than 1.1 mortality odds among COMP-VA patients relative to SOC patients. From an analytical

perspective this means that the upper 95% confidence bound for the fitted odds ratio must be less than 1.1 to reject the null hypothesis that COMP-VA induces extra mortality risks.

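### Both ototoxicity models use arm alone, although planned treatment is read before randomisation; adjusting for planned cisplatin exposure would be a cheap gain in precision

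*SAP*

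**What the plan says.** SAP, Hypotheses to be Tested and Statistical Plan, item 1, gives two analyses of ototoxicity. The first is unadjusted: "Simple analysis will entail computing odds ratios and contrasting these between the COMP-VA and SOC groups". The second is model-based, with one logistic regression for each ototoxicity criterion, and the only term named for these models is arm: they are fitted "with randomization group assignment as predictor". Neither document names a covariate or a stratification factor.

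Protocol A1 describes the population as "An estimated 320 patients from VA Portland Health Care System (VAPORHCS) receiving chemotherapy". The electronic record is searched "to determine the diagnosis and treatment plan and to search for exclusionary criteria". Approach, consent and the first program evaluation follow, and only then allocation: "After the evaluation, if the subject has met all further inclusion criteria, the subject will be randomized to a treatment arm".

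Protocol C3 lists what is entered in the database from the record, including "drug treatment variables such as cisplatin dose and dosing (intensity) and concomitant radiation dose and doublet medication". It does not say when these values are abstracted, or whether they are planned or delivered.

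SAP item 2 links cisplatin to hearing loss and expects COMP-VA to help in part "either through treatment modifications to diminish cisplatin-induced hearing loss".

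**The concern.** The protocol does not fix the anticancer treatment. Patients enter with the treatment their oncology service has planned, so baseline risk of a hearing shift may differ widely between them. If planned cisplatin exposure predicts that risk, an arm-only logistic model leaves explainable variation in the outcome unused and has less power than a model that includes it. The information comes from a record the team already opens at screening.

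Which values are used also matters. Adjustment is safe only with values fixed before randomisation. C3 does not separate planned from delivered treatment, and SAP item 2 makes a change in treatment one route by which COMP-VA may act. A dose variable taken without a date rule could therefore carry part of the intervention's own effect.

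At stake is the precision of the comparison on the hearing outcome, the first outcome listed in the SAP.

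**Working it through.** There is no planned figure to reproduce: the documents give no power, effect size, event rate, allocation ratio or alpha for these models. Only the recruitment estimate of 320 comes from them. Everything else below is an assumption: 1:1 allocation (160 per arm), two-sided 5% tests, and a conditional (within-regimen) odds ratio of 0.5.

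**Step 1. One binary regimen factor, half the patients at higher risk.** In each simulated trial the outcome was analysed by logistic regression on arm alone and on arm plus regimen (3,000 runs per scenario). The regimen odds ratio is the ratio of the two SOC odds, for example (0.60/0.40)/(0.15/0.85) = 8.5.

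| SOC risk, lower / higher regimen | Regimen OR | Power, arm only | Power, adjusted | Gain (points) |
|---|---|---|---|---|
| 25% / 50% | 3 | 75.6% | 78.3% | 2.7 |
| 15% / 60% | 8.5 | 63.1% | 73.0% | 9.9 |
| 10% / 70% | 21 | 50.1% | 67.2% | 17.1 |

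With no treatment effect (15% / 60%), both models rejected in 4.8% of runs.

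**Step 2. Two binary factors, overall SOC risk 50%.** Prevalences were 50% for regimen and 40% for a second factor standing in for radiation (4,000 runs per scenario).

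| Factor ORs | Power, arm only | Power, adjusted | Gain (points) |
|---|---|---|---|
| 1.5 and 1.5 | 83.6% | 84.8% | 1.2 |
| 2 and 1.5 | 82.3% | 83.9% | 1.6 |
| 3 and 2 | 79.1% | 83.1% | 4.0 |
| 5 and 3 | 69.3% | 79.0% | 9.7 |

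Under no effect, rejection was 4.4% to 5.0% across both models.

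**Step 3. Regimen mix.** At 15% / 60%, as the share on the higher-risk regimen rises, the gain falls from about 10 points at 50% to about 5 or 6 at 80%, 1 to 2 at 90% and under 1 at 95%.

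**Step 4. The two odds ratios are different quantities.** Take 15% / 60% with a conditional OR of 0.5.
- Lower-risk regimen: SOC odds 0.15/0.85 = 0.1765; halved, 0.0882, a risk of 8.1%.
- Higher-risk regimen: SOC odds 1.5; halved, 0.75, a risk of 42.9%.
- Averaged over the two halves: COMP-VA 25.5%, SOC 37.5%.
- Marginal OR = (0.255/0.745)/(0.375/0.625) = 0.57.

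The move from 0.50 to 0.57 is non-collapsibility of the odds ratio and occurs with perfect balance. It is not confounding.

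**Step 5. Chance imbalance.** Under simple allocation with a 50% factor, the SD of the between-arm difference is √(0.5 × 0.5 × 2/160) = 0.056. The probability of a difference of 10 points or more is 2[1 − Φ(0.10/0.056)], about 7%. The 5% error rate of the arm-only test already averages over such imbalances.

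**The case against.** The strongest reply is that an unadjusted analysis of a randomised trial is valid, so nothing is broken. That stands. A reader might infer that a chance imbalance in regimen biases the comparison or produces excess false positives. The null simulations show neither, and an unstated randomisation method is not evidence of unstratified allocation.

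The second reply is that the larger gains need strong inputs. That also stands: 17 points requires a regimen odds ratio of 21, and a regimen odds ratio of 3 gives under 3 points. Although A1 recruits chemotherapy patients generally, SAP items 2 and 4 speak of cisplatin treatment and cisplatin patients. If nearly everyone is planned for cisplatin, a yes/no indicator has almost nothing to explain. Planned dose might still vary among them, but that was not simulated.

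Two stronger readings go beyond the documents. One is that planned radiation is known at screening and affects hearing: A1 mentions only the treatment plan, radiation dose appears only in C3 without timing, and no section says that radiation affects hearing. The other is that the plan adjusts for delivered dose. It does not, so the warning about delivered dose is a limit on the fix and not a fault in the SAP.

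Finally, adding a second model without ranking the two would create a choice between results. That is right, and the fix must settle it.

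**Conclusion.** The point holds as a cheap improvement and does not correct an error. SAP item 1 leaves out a baseline predictor that the protocol makes available before randomisation and that the SAP itself regards as causal for hearing loss. The cost is power: about 1 to 17 percentage points across the scenarios in steps 1 and 2, and near zero if planned regimens hardly differ. These figures rest on 320 patients split 1:1, a conditional odds ratio of 0.5, and assumed event rates, regimen shares and prognostic strengths, so the actual gain cannot be determined from the documents. Type I error is about 5% with or without adjustment.

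Confidence is high that the models are arm-only and that the treatment plan is read before randomisation. It is low on the size of the gain.

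**What to change.** In SAP item 1, make the primary model for each ototoxicity endpoint (ASHA, CTCAE) a logistic regression on arm plus planned cisplatin exposure, taken from the record's treatment plan dated before randomisation: cisplatin yes/no, and planned dose where the plan records it. Add planned concomitant radiation only if it is recorded before randomisation.

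Name the adjusted (conditional) arm odds ratio as decisive and keep the unadjusted odds ratio as the simple supporting analysis. State that only pre-randomisation values enter the model, and that delivered dose and later treatment changes do not.

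The cost is a short SAP addition and a date rule for abstraction from a record already searched. The decisive odds ratio becomes conditional and will differ from the marginal one (0.50 against 0.57 in the worked example), so both should be reported and labelled.

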A2. Subject Exclusion Criteria: Subjects must be treated for cancer and must provide a reliable hearing test to be enrolled in the treatment arms of this study. Criteria for excluding subjects (chemotherapy and controls subjects) from this study are: 1) cognitively or physically unable to participate (patient or nurse report patient is incapable of participating), CPRS indication that subject exhibits aggressive behavior, subject has documented dementia, Alzheimer's disease, or severe psychosocial disorder, CPRS notes indicate individual is not legally capable of providing informed consent (subject has a legal guardian); 2) exhibits Meniere's disease or retrocochlear disorder based on hearing test results, patient report or notes in CPRS; 3) exhibits active or recent history of middle ear disorder based on otoscopy, tympanometry, patient report, or notes in CPRS; 4) unwilling to participate; and 6) hearing thresholds > 70 dB SPL at 4 kHz and below (control subjects only).

B. Experimental Techniques. Study measurements are divided into three general groups: Program Evaluation measurements, SOC measurements (Arm 1) and COMP-VA measurements (Arm 2). Measurements in non-clinical controls generally mirror those done for the COMP-VA arm. Testing is done by an Audiologist. The SOC protocol (Arm 1: SOC) is done according to the Audiology Service established protocol. The COMP-VA (Arm 2) protocol includes hearing testing at baseline and at each treatment interval along with a one-month post-treatment evaluation. Testing will be done using OtoID and/or the OtoID-Tablet and/or a standard audiometer. As part of this project, we have developed an updated version of the OtoID which involved migrating to a tablet-controlled device. Like all audiometers, this audiometer is not a medical device since it is "non-invasive" and, therefore, does not require FDA oversight or approval. Rather, the OtoID-Tablet properties are defined and calibrated according to the American National Standards Institute (ANSI) S3.6-2010 "Specification for Audiometers". It was calibrated in 2017 and will be calibrated annually, per ANSI standards.

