B1. PE and Longitudinal Follow-up Measurement: Program Evaluations will be completed in a quiet area and include 1) otoscopy; 2) tympanometry; and 3) hearing threshold testing and 4) the audiologist can elect to include DPOAE testing at any session. Various questionnaires will be given at the discretion of the audiologist. A study team member may request a patient's feedback in the form of a set of mostly open ended questions (Patient Interview Form). A phone call from PE study personnel will be made at regular intervals to inquire about the subject's general well-being, to determine if the

Veteran has experienced any recent noise exposure and retains adequate hearing protection, to ensure that contact information is accurate and not likely to change in the near future, and to remind the Veteran that study personnel will require a final hearing testing session (PE #3). The Veteran may be asked if he/she received any audiological care since the previous contact and requested to bring a report from this contact to the final (longitudinal) program evaluation. Subjects consented and tested may receive a longitudinal follow-up program evaluation depending on their randomization date.

B2. General Procedures for Ototoxicity Monitoring: Attempts will be made to establish baseline results within approximately 24 hrs of treatment. Results from the baseline test will be compared to all subsequent testing for the purposes of ototoxicity detection. Subjects will be provided with education about their hearing, potential changes in hearing and tinnitus associated with ototoxicity and the increased vulnerability of their auditory system to excessive noise exposure for at least a 1-year period after treatment. Disposable-type hearing protection is readily available to subjects at the VA Audiology Clinic and NCRAR.

B2a. Monitoring Procedures for Standard of Care (SOC): Hearing testing will be done according to their established protocol for ototoxicity monitoring in the Audiology Clinic.

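### SAP item 1 predicts smaller hearing shifts at 35 days and 1 year, but no planned analysis compares shift size or uses baseline thresholds

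*SAP*

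**What the plan says.** The prediction is in the SAP, hypotheses, item 1: "the COMP-VA group will have smaller 35 day and 1 year post-randomization hearing shifts compared to SOC patients". It concerns an amount of hearing loss at two times.

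The analyses in the same item are odds ratios, plus one logistic model per criterion "with randomization group assignment as predictor". The criteria are in SAP Outcome Measures, item 1:
- ASHA: "20dB shift at one frequency; 10 dB shift at two consecutive frequencies or loss of response at three frequencies".
- CTCAE Grade 1: "hearing shift of 15-25 dB averaged at 2 contiguous test frequencies in at least one ear".

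The SAP's only comparison of means is the t-test for the hearing handicap score in item 2. Neither item 1 of the hypotheses nor item 1 of the outcomes names the visit, the reference test or the source test for scoring.

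The protocol describes two streams of hearing tests.
- **Program evaluations.** Section A1: "Initial testing to establish inclusion in the study and to provide the first PE will be done in a quiet area". Randomisation follows. Section B1 includes threshold testing in each program evaluation and calls PE #3 the final session.
- **Arm-specific monitoring.** COMP-VA (section B) "includes hearing testing at baseline and at each treatment interval along with a one-month post-treatment evaluation". For SOC (section B2a), "Hearing testing will be done according to their established protocol for ototoxicity monitoring in the Audiology Clinic".

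**The concern.** The prediction is about magnitude, and the analysis is about crossing a threshold. A patient who loses 15 dB and one who loses 50 dB are both simply counted as positive. If COMP-VA limits further loss once a shift has been found, part of its benefit may fall among patients already counted as events. The trial would then close without an estimate in decibels for its first-listed outcome, although it collects thresholds before randomisation and at follow-up.

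A second matter is how the yes/no outcomes are scored. The COMP-VA and SOC monitoring schedules are set differently. Counting a patient as positive if any monitoring test met the criterion would give the more-tested arm more chances to be positive. The SAP does not say that this count is intended, and it does not exclude it.

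**Working it through.** The documents state no power, event rate, SD or allocation ratio for hearing, so there is no planned figure to reproduce. Everything below is illustrative.

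**Assumptions.** Equal arms of 160 (320/2; section A1 gives 320 as an estimate of patients identified, not randomised), two-sided 5%, and shift normally distributed in SD units.

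**1. How the two criteria relate.** Take two neighbouring frequencies with mean shift of at least 15 dB. Either both are at least 10 dB, or one is below 10 and the other is above 20. Each case meets ASHA as worded. The converse fails: 10 and 10 meets ASHA with mean 10, and 0 and 20 does likewise. For measured shifts, CTCAE Grade 1 is therefore the stricter event, and its model can detect loss limited after an ASHA shift.

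**2. Uniform reduction of 0.3 SD.** The COMP-VA rate is 1 − Φ(z(1−p) + 0.3) for SOC rate p. Yes/no power is from the pooled two-proportion test. Mean-shift power is Φ(0.3/√(2(1−r²)/n) − 1.96), where r is the unknown correlation of shift with baseline.

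| SOC rate | COMP-VA rate | Yes/no power, n=160 |
|---|---|---|
| 20% | 12.7% | 43% |
| 30% | 20.5% | 50% |
| 40% | 29.0% | 54% |

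Mean shift: 77% unadjusted (r=0); 78%, 80% and 87% at r = 0.2, 0.3 and 0.5. With 112 per arm (70% of 160): yes/no 32% to 41%, mean shift 61%, adjusted 63% to 74%.

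**3. Benefit starts at the ASHA cut; half of further loss removed.** The ASHA rate is 40% in both arms. With c = z(0.60) and c2 = z(1−r), r now being the SOC CTCAE rate, the COMP-VA CTCAE rate is 1 − Φ(c + (c2−c)/0.5).

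| SOC CTCAE rate | COMP-VA CTCAE rate | CTCAE model power |
|---|---|---|
| 35% | 30.2% | 15% |
| 30% | 21.3% | 43% |
| 25% | 13.7% | 73% |
| 20% | 7.6% | 90% |

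The mean-shift difference is 0.14 SD, with 29% power. The planned CTCAE model is the stronger at three of the four rates.

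**4. Benefit starts only at CTCAE Grade 1.** Both event rates are then equal between arms, so both planned models reject about 5% of the time. Mean-shift power when 50%, 75% or 100% of further loss is removed:
- CTCAE rate 30%: 15%, 29%, 49%.
- CTCAE rate 20%: 8%, 13%, 19%.

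**5. What an ever-met count from monitoring tests would do.** The observed rate is t + (1−t)(1 − (1−e)^k), with true rate t, a false or transient shift in a fraction e of tests, and k independent tests. With t = 30% in both arms and 2 SOC tests (test counts and e are assumed):

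| e | SOC rate | COMP-VA rate, 4 tests | Odds ratio | COMP-VA rate, 6 tests | Odds ratio |
|---|---|---|---|---|---|
| 1% | 0.314 | 0.328 | 1.06 | 0.341 | 1.13 |
| 2% | 0.328 | 0.354 | 1.13 | 0.380 | 1.26 |
| 5% | 0.368 | 0.430 | 1.29 | 0.485 | 1.62 |

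A true odds ratio of 0.66 (22% against 30%) would appear as 0.73, 0.80 or 0.98 with 2 and 4 tests. With equal test counts and no true difference the odds ratio is 1.00.

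**The case against.** **The scoring is already implied.** Protocol section B lists program evaluation as a measurement group separate from both arms' monitoring, and section A1 has patients told that duplicate testing is needed. PE #1 precedes randomisation. PE #3 can be matched to 1 year, because the SAP places the handicap score at both. A PE #2 near day 35 is then a natural inference. This largely stands: common program evaluations are the more natural reading. It remains inference, since no visit is tied to day 35 and the SAP does not name the reference.

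A reader might infer the opposite, that the hearing comparison is biased against COMP-VA because that arm is tested more often. The text nearest to this is "Results from the baseline test will be compared to all subsequent testing for the purposes of ototoxicity detection". It stands in section B2 on monitoring procedures and governs detection, not the comparison of arms. The odds ratios in step 5 therefore apply only if someone chooses an ever-met count. Even then, the additional testing that section B2b allows after a suspected change would reduce them.

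**The yes/no models are enough.** Steps 3 and 4 support part of this: the CTCAE model is often stronger than mean shift, and mean shift has modest power where both planned models have none. The 0.3 SD in step 2 has no source in the documents. Rewording the prediction as lower ototoxicity rates would also end the mismatch. That is a fair minimum, but the size of the effect would stay unreported, although the thresholds are collected.

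**Covariates are a preference.** Agreed: leaving them out costs precision, not validity.

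**Conclusion.** The point holds as a mismatch between a stated prediction and its analysis that is cheap to repair. Item 1 predicts smaller shifts at two times; no analysis compares shift size, and the PE #1 thresholds are not used for adjustment. This rests on the text alone.

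The size of the loss cannot be fixed from the documents. At 160 per arm it ranges from a clear gain for mean shift (77% against 43% to 54% under a uniform 0.3 SD reduction) to a clear advantage for the planned CTCAE model (90% against 29% in the most favourable case of step 3). The case for adding a shift analysis is that it answers the question the SAP poses, not that it always has more power.

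Two stronger readings are not supported. The planned models are not invalid: they are sound under randomisation and test the prediction in part. Nor do the documents show that unequal testing biases the hearing result, because they point towards common program evaluations. Naming those evaluations confirms that reading and closes off the alternative.

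**What to change.** 1. Add a between-arm comparison of threshold shift from PE #1, over a fixed set of frequencies, adjusted for baseline threshold and age, at PE #3 (1 year). Do the same at day 35 if both arms have a program evaluation then; otherwise drop the day-35 claim.
2. State a rule for frequencies with no response, with a sensitivity analysis. ASHA as worded covers lost responses; the CTCAE wording does not.
3. Keep the ASHA and CTCAE models. State that both arms are scored from the same program evaluations against PE #1, not from the arm-specific monitoring tests.
4. Optionally add baseline pure-tone average and age to the logistic models for precision, and report adjusted beside unadjusted odds ratios.
5. Report by arm how many subjects lack each evaluation and why, including death. Section B1 makes the longitudinal evaluation depend on randomisation date.
6. The SAP outcomes section is in the past tense. If results are already known, label the added analyses post hoc.

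**Cost.** SAP wording and modest extra analysis. The 1-year comparison needs no new data where PE #3 was done; the day-35 comparison needs a test near that day in both arms. The drawbacks are that the shift result depends on the no-response rule, the adjusted odds ratio is less simple to interpret, and mean shift is not always more powerful than the planned CTCAE model.

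### The one-year HHIE/HHIA t-test makes no use of pre-randomisation hearing thresholds or age, which the trial already collects and which could sharpen the comparison

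*SAP*

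**What the plan says.** **The analysis.** SAP, Hypotheses, item 2 takes as its outcome the "HHIE or HHIA questionnaire administered at 1 year post-randomization" and states: "We will conduct a t-test with randomization arm as the contrast to test the importance of COMP-VA on perceived quality of life outcomes". Neither document names a covariate for this comparison. SAP, Outcome Measures, item 3 defines the outcome as a score at the third Program Evaluation (PE 3), not a change from baseline. The version of the questionnaire is chosen "depending on the age of the subject) at PE 3 were evaluated".

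**What is available before randomisation.**
- Protocol A1: "Initial testing to establish inclusion in the study and to provide the first PE will be done in a quiet area". Allocation comes next: "After the evaluation, if the subject has met all further inclusion criteria, the subject will be randomized to a treatment arm".
- Protocol A2: subjects "must provide a reliable hearing test to be enrolled in the treatment arms of this study".
- Protocol B1: "Program Evaluations will be completed in a quiet area and include 1) otoscopy; 2) tympanometry; and 3) hearing threshold testing".
- Protocol C3: "Information to be obtained will include patient factors such as name, gender, age", taken from the medical record.

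**The concern.** Read together, Protocol A1, A2 and B1 imply that every randomised patient has hearing thresholds measured before allocation, so arm cannot have influenced them. Age may be abstracted from the record later, but its value is fixed at randomisation. Both are therefore sound covariates for a randomised comparison.

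The documents also suggest that they are relevant to the outcome. SAP hypothesis 2 counts deficits present before treatment among the sources of perceived handicap. The sample includes both previous hearing-aid users and non-users. The 70 dB threshold limit in Protocol A2 applies to controls only, so it does not narrow the range of baseline hearing among randomised patients.

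An outcome measured once at one year and compared by arm alone leaves all of that between-patient variation in the error term. What is at stake is a wider confidence interval and lower power than the collected data might allow. The treatment estimate is not biased by this choice.

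**Working it through.** The documents state no power calculation, alpha, SD, effect size or correlation for this test, so there is no figure to reproduce. What follows is an illustration.

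**Assumptions**
- True difference 0.3 SD; two-sided 5%; equal arms.
- Two covariates (k = 2): a pure-tone average from the first PE, and age. Their multiple correlation with the PE 3 score is r.
- Patients with a PE 3 score: 100, 84 or 60 per arm. The middle value takes the 320 chemotherapy patients in Protocol A1 and assumes 70% alive at one year, with 75% of those reaching PE 3: 320 × 0.70 × 0.75 = 168, or 84 per arm. Neither rate is in the documents. The 320 are patients to be identified, so the number randomised may be smaller.

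**Formulas**, with N the total analysed and n = N/2
- Variance relative to the unadjusted test: V = (1 − r²) × [1 + k/(N − k − 3)]. The bracket is the price of estimating two covariate effects.
- Power: noncentral t with N − 2 − k degrees of freedom and noncentrality 0.3 × √(n/2) / √V. The unadjusted test has V = 1 and N − 2 degrees of freedom.
- Break-even r, where the variance gain equals the price: √(1 − 1/bracket).

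**Worked case, 84 per arm, r = 0.3**
- Bracket: 1 + 2/163 = 1.012.
- V = 0.91 × 1.012 = 0.921, a net variance reduction of 7.9%.
- Noncentrality: 0.3 × √42 = 1.944 unadjusted; 1.944/√0.921 = 2.026 adjusted.
- Power: 48.9% unadjusted, 52.2% adjusted.
- 95% CI half-width: 1.974 × √(2/84) = 0.305 SD unadjusted; 0.305 × √0.921 = 0.292 SD adjusted, about 4% narrower.

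**Power over the range** (change in percentage points from the t-test in brackets)

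| Per arm | t-test | r = 0 | r = 0.1 | r = 0.3 | r = 0.5 | Break-even r |
|---|---|---|---|---|---|---|
| 100 | 56.0% | 55.6% (−0.4) | 56.0% (0.0) | 59.6% (+3.5) | 67.9% (+11.9) | 0.10 |
| 84 | 48.9% | 48.5% (−0.5) | 48.8% (−0.1) | 52.2% (+3.2) | 60.2% (+11.3) | 0.11 |
| 60 | 37.1% | 36.6% (−0.5) | 36.9% (−0.2) | 39.5% (+2.4) | 46.2% (+9.2) | 0.13 |

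Changes are computed before rounding.

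**Sensitivity to the effect size.** At 84 per arm and r = 0.3, the gain is 1.7, 3.2, 3.4 and 2.2 points for true differences of 0.2, 0.3, 0.4 and 0.5 SD.

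**Simulation check.** With 20,000 simulated trials per setting at 84 per arm, power of the t-test and of ANCOVA was 48.3% and 47.7% (r = 0), 48.6% and 48.7% (r = 0.1), 49.0% and 52.3% (r = 0.3), and 48.7% and 60.1% (r = 0.5). This agrees with the table.

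**The case against.** The strongest reply is that nothing here is wrong. An unadjusted t-test is a legitimate pre-specified choice, it matches the arm-only models elsewhere in the SAP, and the documents do not establish that adjustment would help. Over the range above, the change runs from slightly negative to about 12 points, and the middle case is a CI about 4% narrower. That is fair. It is why this is an efficiency point with an unknown and probably modest gain. It does not remove the asymmetry: the loss is about half a power point at worst, and break-even needs a correlation of only 0.10 to 0.13.

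Three further objections stand in part.
- **Missing outcomes.** Validity is claimed only for complete data. Protocol B1 makes the longitudinal evaluation conditional on randomisation date, and the SAP gives no rule for patients without a PE 3 score. In the illustration, 320 − 168 = 152 patients have none. Adjustment does not settle that problem, nor whether HHIE and HHIA scores can be pooled.
- **Test frequencies.** Neither document lists the frequencies tested at a PE. Thresholds are collected, but whether a particular average can be formed must be checked against the data.
- **Timing.** SAP, Outcome Measures, speaks of outcomes already evaluated by arm, while hypothesis 2 is in the future tense. If results by arm have been seen, replacing the t-test would be post hoc.

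**Conclusion.** The concern holds. The planned comparison ignores two variables fixed before randomisation that the trial already collects, one of which, hearing thresholds, should exist for every randomised patient. The t-test is not in error; it may be less precise than it could be.

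At an assumed multiple correlation of 0.3, adjustment cuts variance by about 8% and adds roughly 2 to 4 power points for a 0.3 SD difference with 60 to 100 patients per arm. At 0.5 it adds 9 to 12 points. At zero it costs about half a point. The correlation, effect size and number analysed are all assumptions, so confidence in the size of the gain is limited. The case for the change rests on its low cost and small downside, not on a demonstrated large loss.

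**What to change.** Analyse the PE 3 score by ANCOVA on arm, one pure-tone average from the first PE, and age in years, and report the unadjusted t-test alongside. Define the average in advance: the frequencies, how the two ears are combined, and how frequencies with no response are handled. One example is the mean over both ears at 0.5, 1, 2 and 4 kHz, provided those frequencies were tested.

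Use the first PE, not the monitoring baseline, which Protocol A1 places after arm assignment. Add baseline hearing-aid use or a baseline HHIE/HHIA score only if it was recorded in both arms before randomisation; Protocol B1 leaves questionnaires to the audiologist's discretion, so a baseline score is not assured.

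State in the SAP whether outcomes by arm had been seen when the text was written. If they had, keep the t-test as the stated analysis and label the ANCOVA supplementary.

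The cost is SAP wording, plus a check of which frequencies the first PE recorded. If a usable set was recorded, no new measurement is needed.
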